Effects of a walking program and inspiratory muscle training

**Effects of a Walking Program and Inspiratory Muscle Training
on Individuals with Chronic Heart Failure**

(ClinicalTrials.gov identifier :NCT01560871)

12/2/2013

Protocol Title

Effects of a walking program and inspiratory muscle training on individuals with chronic heart failure - a pilot study

1) Investigator

[name], PT, PhD

2) Objectives

The purpose of this pilot study is to examine the effects of inspiratory muscle training (IMT) plus home-based walking program in individuals with chronic heart failure. The primary outcomes are: respiratory muscle strength as indicated by maximal inspiratory pressure (P_Imax), cardiovascular endurance (indicated by the six-minute walk test distance), autonomic function (indicated by the heart rate variability) and health-related quality of life. We hypothesize that both groups will have improvements in P_Imax, cardiovascular endurance, heart rate variability, and quality of life, and that the extent of improvements will be greater for the experimental group (high-intensity IMT) than the sham group (low-intensity IMT). We plan to recruit patients who are discharged within 6 months after acute illness, since these patients may be medically stable and mobility independent, but their overall exercise capacity may not be ready for full function in the community yet.

3) Background

Prevalence of heart failure is approximately 1% ^[1]. The leading causes of heart failure are coronary artery disease, hypertension and diabetes. Other causes include cardiomyopathy, heart valve disease, arrhythmia and congenital heart disease. Patients often develop symptoms when all compensatory mechanisms fail to provide adequate cardiac output of the heart. General fatigue and dyspnea with exercises often reduce their desire for physical activity. Deconditioning and dyspnea eventually becomes a vicious cycle. Health care cost for patients with heart failure is skyrocketing due to its repetitive, costly, and prolonged hospitalization. ^[2] With an increasing elderly population, it is estimated that the burden of care would continue to increase for heart failure.

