- iii) It will be emphasized that their participation in the study is completely voluntary, and it will not affect their medical treatments in any ways.
- iv) Participants will be paid a total of \$50.

- v) A total of 30 subjects will be enrolled from the Presbyterian Hospital of Dallas, excluding screening failure.

b) Inclusion and Exclusion Criteria

- i) Subjects inclusion criteria:
 - (1) adults with chronic heart failure (NYHA Functional Class II-III) who are just discharged from an acute care hospital in the past three months,
 - (2) with BMI < 35 kg/m²,
 - (3) greater than 18 years of age,
 - (4) walk independently with or without assistive device.
(note: According to New York Heart Association's Functional Classification, patients who have reasonable compensatory ventricle remodeling and relatively normal cardiac output at rest and with inadequate increase in cardiac output upon exertion belong to Class II and III, whereas those with inadequate cardiac output at rest will be classified as NYHA Class IV.)
- ii) The total expected number of subjects needed to complete the study is 50 excluding those screen failure. Thirty subjects will be recruited from the Presbyterian Hospital of Dallas.

c) Study Endpoints

- i) The primary study endpoint will be that 30 participants complete all evaluations, reassessment, and 6-week of training program. The secondary study endpoint would be all data management is completed.
- ii) The primary safety endpoint would be that participants complete all study protocols without adverse responses. The secondary safety endpoint could be all research data get kept and protected 10 years accordingly.

d) Procedures involved in the Human Research

- i) This study will be a double-blind randomized controlled study. Evaluators will not be aware of subject's group assignment. Each subject does not know group assignment either
- ii) Timeline of the procedures
 - (1) Recruitment: Two research coordinators screen medical charts to identify potential subjects
 - (2) initial evaluation
 - (a) History taking
 - (b) set up ECG electrodes on the holter monitor unit to monitor heart rhythm throughout the session,
 - (c) maximal inspiratory muscle strength test (P_{Imax})
 - (d) Grip strength test
 - (e) 2-min comfortable walking speed test
 - (f) single limb stance test at eyes open and eyes closed conditions
 - (g) rest for 15 minutes (supine – standing - supine, 5 min each)

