Effects of a walking program and inspiratory muscle training

- (h) 6-minute walk test on a hallway- first trial: assess subject's physiologic responses closely
 - (i) resting for 15-20 minutes in sitting and completing two surveys
 - (j) 6-minute walk test – 2nd trial : monitor subject's physiologic responses closely
 - (k) give a pedometer, an accelerometer, a breathing device, a heart rate monitor
- (3) exercise training program at home
- (a) for participants :
 - (i) daily walking routine: record daily step counts, duration of breathing exercise, and training target of P_Imax in the log
 - (ii) weekly follow-up for re-assessment of P_Imax at heart failure clinic or at the research participant's home
 - (b) for researchers:
 - (i) ask subjects for any concerns/difficulties during walking program and breathing exercise at weekly follow up: determine whether to continue the study or discontinue
- (4) final evaluations : repeat the same tests as those done during the first visit

iii) Procedures:

The initial evaluation session will last approximately two hours which will include the interview to gather basic demographic and medical data such as names, telephone number, complete address, email address, dates of treatments and birth date, medications, height, weight, age, and past medical history. After the interview, we will measure the maximal inspiratory pressure (P_Imax) that the subject can generate by a pressure threshold spirometer (Micro Direct, Inc. ME 04240), which is directly related to respiratory muscle strength. Then, the individual will be connected with a holter monitor to monitor their heart rate activity.

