Since most individuals with heart failure are older than 50 years of age, so we include 3 outcomes specific to older people. (1) Grip strength: A dynamometer for grip strength will be used for 3 trials. (2) Single limb stance test at both eyes open and eyes closed conditions. The time to maintain single limb stance will be recorded for 3 trials at both conditions. (3) Comfortable speed: the participant will be asked to walk at their comfortable speed back and forth over a 44-foot segment of hallway for two minutes. The times for completing the 44-foot distance will be measured. Heart rate variability will be recorded during the above 3 outcome measures. After these measures, the participant will rest for 15 minutes in the following positions: supine (5 min), standing (5 min), then in supine again (5 min). The holter monitor will continue to monitor their heart rate activity when resting in these 3 positions.

After rest, we will set up telemetry ECG system and administer the six-minute walk test. The participant will be instructed to walk for 6 minutes and to cover as much distance as they can. The distance walked, symptoms and signs of exercise intolerance will be monitored and recorded. After the first trial, the participant will be

allowed to rest for about 15 minutes to allow heart rate returns to initial baseline (+/- 5 beats). During this rest period, we will have the participant fill out the 2 questionnaires (Minnesota Living with Heart Failure Questionnaire and SF36 Questionnaire). Then, we will repeat the six-minute walk test to account for learning effect. The SF-36 questionnaire asks a question regarding sexual difficulties. Subjects can refuse to answer if they find it uncomfortable.

All the initial outcome evaluations will be repeated after 6 weeks. There will be two research team members doing the evaluations and another two research team members conduct the weekly re-assessment.

Each participant will be unknowingly assigned to one of the two groups: (1) a walking program with a sham (low-intensity) Inspiratory Muscle Training (IMT) protocol, and (2) a walking program with a real (high intensity) IMT at 60% of maximal inspiratory pressure (P_Imax). Research team members who conduct evaluations will be blinded to the group assigned. Only the primary investigator and those research members who conduct the weekly re-assessment of P_Imax know the group assignment.

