Each participant will be given an accelerometer to track their 7-day physical activity for the first and the last week of training. The home-based walking program will consist of walking at an intensity of “somewhat hard” to “hard” on the Rating of Perceived Exertion (RPE) scale. Participants will be educated on the 10-point RPE scale to judge their fatigue level. For example, at rest, they would rate their exertion level as “nothing at all” which is equivalent to “zero” on the RPE scale. If they were very tired and shortness of breath after any exhausted activities such as climbing two to three flights of stairs, they probably rate their exertion level as “very, very, very hard.” The scale has been shown to be highly related to a person’s heart rate. They will be advised to slow down if they feel their exertion level is toward the “very hard” level. Participants will begin walking at least 15 minutes twice a day, or as tolerated, for 7 days a week and eventually progress to 45-50 minutes a day by six weeks. They will also be instructed to wear a simple pedometer each day to record step counts. During their weekly re-assessment visit, a research team member will calculate the “mean” and “standard deviation” of their previous 7-day step counts. They are encouraged to reach the mean step counts for the following week; however, if they are tired on a specific day, they are encouraged to at least reach the lower target (e.g., the mean minus one standard deviation of previous week’s step counts). We found this approach to be effective based on a case study.

For the IMT, the training threshold will be set at 60% of P_Imax (maximal inspiratory pressure) for the experimental group. The participant will perform the breathing exercise one session daily with a nose clip used, so the participant breathes completely through the mouth. The 6 Interval Levels: (6 inspiratory efforts in each level): (1) 60s rest interval; (2) 45s rest interval; (3) 30s rest interval; (4) 15s rest interval; (5) 10s rest interval; (6) 5s rest interval, trained to exhaustion. The sham IMT group will be trained at fixed 15% P_Imax which is lower than the training threshold

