(i.e., 30% P_Imax) reported in the literature. The time commitment for their IMT exercise is about 15-20 minutes per day for both groups. Each participant will have weekly follow up visit which can be done either at our facility or a research team member will do a home visit for about 15 to 20 minutes to reassess their new P_Imax and reset the new IMT intensity for the following week. In addition, the research team will record their ambulatory activity of the previous week.

Study will be conducted in the research suite (8th floor) at the T. Boone Pickens Institute of Health Sciences – Dallas of TWU. There will be no other personnel in the area except the research team members. The weekly sessions for reassessment of respiratory muscle strength will be conducted in the research suite on TWU-Dallas campus, at the outpatient heart failure clinic of the PHD, or at the patient's home whichever is convenient for the participant.

e) Data management

- i) The PI, research coordinators, and research graduate assistants will be responsible for data collection and transmission of data.
- ii) No specimens will be collected.
- iii) Data will be transferred from the hard copies of data collection forms to the password protected computer for further data management with Excel program and SPSS statistical software.
- iv) Only subjects' initials and other study related findings will be record in the data forms. During data management, only codes will be used. For example, each participant will be coded as "group number + subject number" (e.g., C-1 (control group, subject 1); E-1 (experimental group-subject 1)). An excel file containing the master list of subjects' initials and codes will be kept in a password protected computer. The data will be stored in a locked cabinet at Room 5610, School of Physical Therapy of the TWU- Dallas campus. Only the research team members have access to the data. All data will be coded. The data will be stored for 10 years after completion of the study and it will be destroyed after 8/31/2023.
- v) Data Analysis: Two-way (group x time) repeated measure ANOVA (or multivariate ANOVA) will be used to compare the primary and secondary outcome measures between the 2 groups (sham IMT vs. real IMT) and across the 2 time points (pre- vs. post-training). The PI will consult a statistical consultant for final data analysis in the future.

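### Walking targets are set, and probably encouraged, at a weekly visit run by staff who know the arm; the encouragement is not standardised, so unequal walking could shift six-minute walk distance

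*Combined protocol and SAP*

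**What the plan says.** Section 2 (Objectives) lists four primary outcomes, among them "cardiovascular endurance (indicated by the six-minute walk test distance", and predicts larger gains in the high-intensity arm.

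On blinding, section 6(d)(i) states: "This study will be a double-blind randomized controlled study". It then explains that evaluators and subjects are unaware of assignment. Section 6(d)(iii) says who is aware: "Only the primary investigator and those research members who conduct the weekly re-assessment of P_Imax know the group assignment". Section 5(d) and section 6(d)(iii) give the evaluations to two team members and the weekly re-assessments to two others.

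On walking, section 6(d)(iii) gives a starting dose: "Participants will begin walking at least 15 minutes twice a day, or as tolerated". This is to build up to 45-50 minutes a day by six weeks. For step counts: "During their weekly re-assessment visit, a research team member will calculate the" mean and standard deviation of the preceding seven days. Then: "They are encouraged to reach the mean step counts for the following week". On a tired day the lower target is the mean minus one standard deviation. At the same contact, section 6(d)(ii)(3) has researchers "ask subjects for any concerns/difficulties during walking program and breathing exercise at weekly follow up" and decide on continuation.

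On walking data, section 6(d)(iii) provides a daily pedometer record, an accelerometer in the first and last training weeks, and, at each weekly visit, "the research team will record their ambulatory activity of the previous week". Section 6(e)(v) plans a group-by-time ANOVA of the primary and secondary outcomes. The document does not list the secondary outcomes.

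**The concern.** The comparison isolates IMT only if walking is delivered alike in both arms. Walking is also the activity that the six-minute walk test measures. The weekly visit brings together staff who know the arm, a stated expectation about which arm should do better, and open-ended encouragement to walk.

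If one arm were encouraged more, its members might actually walk more and improve more. A blinded evaluator would then measure a real difference accurately, but the difference would mix IMT with extra walking. Because each week's mean becomes the next week's target, an early difference could carry forward through the six weeks. Without a pre-specified account of walking by arm, a reader of the result could not tell whether this had happened.

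**Working it through.** **The chain of statements**

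| Link | Source | Status |
|---|---|---|
| Weekly re-assessment staff know the arm | 6(d)(iii) | Stated |
| Step target is calculated at that visit | 6(d)(iii) | Stated |
| The same staff give the encouragement | 6(d)(iii) with 5(d) | Natural reading; the speaker is not named |
| Target formula is the same in both arms | 6(d)(iii) | One rule given, no arm distinction |
| Wording and intensity of encouragement, and advance in minutes, are standardised | 6(d)(iii) | No script or procedure given |
| Walk distance is a primary outcome | Section 2 | Stated |
| Walking is compared by arm | 6(e)(v) | Unspecified; secondary outcomes not listed |

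**Size**

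The documents give no figure for this bias, so there is none to reproduce. The group sizes come from section 6(e)(vii): 15 per group from the power statement and about 25 per group enrolled. The 15 cannot be uniquely reproduced, because the design effect size, alpha and sidedness are not stated. At two-sided 0.05 and 80% power it corresponds to a standardised difference of about 1.02 (normal approximation) to 1.06 (t). The point here does not depend on that derivation.

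Assumptions: true IMT effect zero, two-sided alpha 0.05, and unequal walking adds a spurious shift of b standard deviations. With two time points, the group-by-time test is equivalent to a t test on change, so b is in SD of the change in distance.

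Formula: rejection probability = P(|T| > t(0.975, 2n-2)), where T is noncentral t with 2n-2 degrees of freedom and noncentrality b × √(n/2).

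- n = 15: √(15/2) = 2.739, 28 degrees of freedom.
- n = 25: √(25/2) = 3.536, 48 degrees of freedom.

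| b (SD) | Noncentrality, n=15 | P(p<0.05), n=15 | Noncentrality, n=25 | P(p<0.05), n=25 |
|---|---|---|---|---|
| 0 | 0 | 5.0% | 0 | 5.0% |
| 0.1 | 0.274 | 5.8% | 0.354 | 6.4% |
| 0.2 | 0.548 | 8.3% | 0.707 | 10.7% |
| 0.3 | 0.822 | 12.5% | 1.061 | 18.0% |
| 0.4 | 1.095 | 18.5% | 1.414 | 28.3% |

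The 18.5% entry is 18.48% before rounding, hence 18% as a whole number.

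Sensitivity to the scale: suppose b is instead in SD of distance at one time point, with an assumed pre-post correlation of 0.7. The shift in SD of change is then b/√(2 × (1 - 0.7)) = b/0.775. For b from 0.1 to 0.4 the rejection probability becomes 6.3% to 27.7% at n = 15 and 7.3% to 43.2% at n = 25.

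**The case against.** The strongest reply is that staff have little room to influence walking. Both step targets come by formula from the participant's own counts. The main target is last week's mean, which asks for maintenance and not an increase. The lower target depends on whether the participant is tired that day, exertion is self-rated, and section 7(a) ties progression to the participant's own tolerance. Participants are blinded. The visit lasts about 15 to 20 minutes and includes re-measuring inspiratory pressure and resetting the device. Staff who reset the load have to know the arm, and this is a pilot.

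Much of this stands. It removes the target itself and the fallback target as routes for bias. It leaves the tone and content of the encouragement, and whatever staff say about advancing the minutes. The pilot label does not dispose of the point, because section 2 states a between-arm efficacy hypothesis and section 6(e)(vii) a power justification.

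Three stronger readings are tempting, and the documents support none of them.

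- **That one arm is in fact pushed harder.** Nothing shows this, and that arm-aware staff do the encouraging is itself an inference.
- **That no arm comparison of walking is planned.** The secondary outcomes are never listed, so the comparison is unspecified, not shown to be absent. The first- and last-week accelerometer data would fit a two-time-point analysis, although the first week is already on training.
- **That any step difference is contamination.** Steps are measured after randomisation. Section 3 (Background) links respiratory muscle dysfunction to exercise intolerance, and section 6(e)(vii) cites improved dyspnea after IMT. More walking may therefore be an effect of IMT.

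**Conclusion.** The concern holds as an unprotected route for performance bias, not as a demonstrated bias. The arm-aware staffing, the target set at their visit and the exposed primary outcome are all stated; who gives the encouragement is the natural reading.

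The magnitude is unknown. Over the assumed range of 0.1 to 0.4 SD, the false-positive chance for walk distance is 6-18% at 15 per group and 6-28% at 25. The lower end is barely above nominal, and nothing in the documents anchors the range. The case for acting rests on the mechanism and the low cost of closing it. Standardisation has to be in place before the visits begin, because it cannot be recovered at analysis.

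**What to change.** In section 6(d)(iii), state that the weekly step target, computed by the existing formula, is handed over on a printed card with one fixed encouragement wording used in both arms. State also that the protocol's existing safety, tolerance and continuation contact is unchanged: the weekly questions about difficulties, the decision to continue, and the advice about exertion.

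In section 6(e)(v), pre-specify a by-arm report of weekly mean steps and of first- and last-week accelerometer activity, presented beside the six-minute walk result. Do not adjust walk distance for steps, since steps may lie on the path from IMT to the outcome. State in advance that a step difference may reflect either unequal coaching or an effect of IMT.

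The cost is a one-page script and one extra table from data already being collected. The downside is slightly less tailored encouragement.

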- c) The Physical Therapy program at TWU-Dallas campus has the equipment and the research space needed for this study. The campus is located in an 8-floor building which was opened in 2011 and housed a few health sciences programs such as nursing, occupational therapy, and physical therapy programs. There are several new equipment and research labs in the building for interdisciplinary research related to qualitative and quantitative studies. There is also a counseling clinic with two experienced clinical psychologists who can provide psychological consultation if needed. There are a few AED (automated external defibrillator) available on certain locations of the campus. In addition, across the street of the campus is the St. Paul Hospital, researchers can send the participant there in case he/she requires medical care as a consequence of the Human Research.
- d) The PI will oversee all research activities of the study. There are four DPT graduate students helping with this study involving evaluations, reassessment, data collection, and data analysis. They participate in this project as a requirement of their “Critical Inquiry” courses under the supervision of the PI at the TWU-Dallas campus. They have taken courses related to research methodology and cardiopulmonary physical therapy, and the NIH Human Subjects Protection Training. The PI is an experienced physical therapist whose expertise is in the management of patients with cardiac or/and pulmonary conditions. The research team members are familiar with ECG interpretation and assessment of exercise intolerance. They also had practiced the study protocol a few times to ensure they are skilled in conducting all procedures efficiently and safely. Two of them will conduct the evaluations and the other two research members will conduct the weekly re-assessment. The evaluators will be blinded to the group assignment.

6) Study Design

a) Recruitment Methods

- i) Potential subjects will be identified via medical charts by two research coordinators at the PHD.
- ii) Potential subjects will be approached via one of the two ways: (1) when discharging from the inpatient heart failure unit, the inpatient research coordinator, [name], will talk to potential subjects about the study; or (2) when they return to the outpatient heart failure clinic for follow up, the outpatient research coordinator, [name], will talk to them about the study.

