- a) Possible risks include fatigue, overexertion, or loss of confidentiality. The fatigue or overexertion could occur during their daily walking program or breathing exercise which will last only a few minutes. Subjects will be advised to judge their tolerance with these exercise, then progress the intensity and duration gradually according to their own tolerance.
- b) Risks such as embarrassment from filling out sensitive questionnaires could happen. If a subject finds any questions in the survey or questionnaire discomfoting, he/she does not have to answer that question.

8) Potential benefits to subjects

Subjects will benefit from free access to the breathing exercise training program and individually tailored walking program. They may improve their exercise tolerance and breathing strength through the study. A free pedometer, a heart rate monitor, and a breathing device will be provided to them for free. Each subject will also receive \$25 at the initial evaluation and another \$25 at the final visit after 6 weeks of home-

based training.

9) Provisions to protect the privacy interests of subjects

The evaluations and weekly follow-up will be conducted in a private room or space where only the participant and research team members are present, except when they are performing the walking tests on a hallway. No other personnel will be allowed in the interview area.

10) Provisions to maintain the confidentiality of data

a) The data will be coded. For example, each participant will be coded as "group number + subject number" (e.g., C-1 refers to control group-subject 1); E-1 refers to experimental group-subject 1). An excel file with the master list linking subjects' initials and codes will be stored in a password protected computer. Only research team members have access to the computer. During most of the data management processes, only the codes will be used.

b) The data will be stored in a locked cabinet in Room 5610 at the School of Physical Therapy of the TWU- Dallas campus. Only the research team members have access to the data. The data will be stored for 10 years after completion of the study and it will be deleted from the computer and hard copies will be shredded after 8/31/2023.

11) Medical care and compensation for injury

N/A - this study only involves minimal risks to research participants

12) Cost to subjects

This walking program and breathing exercise will be free to research participants in the study.

13) Consent process

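### Participant IDs that state the arm, with team-wide data access that does not exclude the evaluators, leave the promised evaluator blinding unprotected

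*Combined protocol and SAP*

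**What the plan says.** **Blinding.** Section 6(d)(i): "This study will be a double-blind randomized controlled study" and "Evaluators will not be aware of subject's group assignment". Section 5(d), on staffing, repeats it: "The evaluators will be blinded to the group assignment". Section 6(d)(iii) says who may know: "Only the primary investigator and those research members who conduct the weekly re-assessment of P_Imax know the group assignment".

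**Who the evaluators are.** Section 6(d)(iii): "There will be two research team members doing the evaluations and another two research team members conduct the weekly re-assessment". Section 5(d) identifies all four as graduate students. It lists evaluation, reassessment, data collection and data analysis as their joint work, and then splits only the first two tasks between pairs.

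**Coding.** Sections 6(e)(iv) and 10(a) define the ID as group plus subject number, illustrated by "C-1 (control group, subject 1); E-1 (experimental group-subject 1"). Paper data forms carry initials; the codes are used during data management. A spreadsheet links initials to codes.

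**Access.** Sections 6(e)(iv) and 10(b): "Only the research team members have access to the data". Section 10(a), on the computer that holds the master list: "Only research team members have access to the computer".

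**The concern.** The first character of the ID gives the arm, so anyone who sees a coded record, or looks up initials in the master list, knows the allocation. The people allowed to do this are the research team, and the evaluators belong to it.

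The outcome tests are repeated at 6 weeks, while recruitment is planned over a year. Coded data from a participant's first visit can therefore exist before that participant's second evaluation, and nothing delays coding until then.

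Four primary outcomes are named in section 2. Maximal inspiratory pressure and six-minute walk distance depend on effort, and a tester who knows the arm can influence them through encouragement. Heart rate variability is recorded by Holter monitor and the quality-of-life forms are self-completed, so both are less exposed. Bias introduced this way cannot be removed in the analysis.

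**Working it through.** **Text check.** The point is mainly textual.

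| Question | What the documents give |
|---|---|
| Does the ID reveal the arm? | Yes: 6(e)(iv) and 10(a) |
| Is there a key from initials to ID? | Yes: the master list in 6(e)(iv) and 10(a) |
| Who may reach data and computer? | The research team: 6(e)(iv), 10(a), 10(b) |
| Are evaluators in that group? | Yes: 6(d)(iii) |
| Who may know the arm? | Investigator and weekly re-assessors: 6(d)(iii) |
| Are evaluators kept out of data tasks? | Not stated: 5(d) lists these tasks for all four students, and 6(e)(i) gives data collection and transmission to the graduate assistants among others |
| Is there a neutral ID, a restricted file, a separate data-entry role or delayed coding? | None found |

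The group with access is wider than the group allowed to know the arm, and the difference includes the evaluators.

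**Possible size.** The plan has no figure to reproduce. The calculation below is illustrative.

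- From section 6(e)(vii): n = 15 per group (the calculated size) or 25 per group (planned enrolment, raised for dropout).
- Assumed: no true effect; two-sided 5% test; coaching adds b = 0.2 to 0.5 SD of the pre-to-post change to the group difference; a share f of participants is affected.
- Test: two-sample t-test on change scores, which is equivalent to the group-by-time interaction in the planned two-way ANOVA when there are two time points.
- Noncentrality: λ = f × b × √(n/2), with √7.5 = 2.739 for n = 15 and √12.5 = 3.536 for n = 25.
- Rejection rate: P(|T| > t_crit), with T noncentral t on 2n − 2 degrees of freedom; t_crit = 2.048 (28 df) or 2.011 (48 df).

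Worked case: n = 15, f = 0.5, b = 0.5 gives λ = 0.25 × 2.739 = 0.685 and a rejection rate of 10.1%.

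| Share affected | 15 per group, b = 0.2 to 0.5 | 25 per group, b = 0.2 to 0.5 |
|---|---|---|
| 0 | 5.0% | 5.0% |
| 0.25 | 5.2% to 6.3% | 5.3% to 7.2% |
| 0.5 | 5.8% to 10.1% | 6.4% to 13.9% |
| 1 | 8.3% to 26.2% | 10.7% to 41.0% |

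A simulation of 200,000 runs, shifting a random half of the experimental arm by 0.5 SD, gave 9.9% at 15 per group and 13.6% at 25. These are close to the formula's 10.1% and 13.9%.

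**The case against.** The strongest reply is that the access statements are confidentiality limits: they keep outsiders out and need not give every team member every file. Section 6(d)(iii) has the specific rule on who knows the assignment, and a specific rule can be read as limiting a general one. Evaluation and reassessment are staffed by different people. Forms carry initials, so nothing on an evaluator's form shows the arm. No text says that evaluators enter data or open the master list.

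Much of this stands. The two rules can be read as compatible, and leakage is a possibility, not a described event. But the specific rule states an intention and no mechanism carries it out. Evaluators can be expected to know their participants' initials, and the shared list turns initials into arm. A password separates the team from outsiders; it does not separate evaluators from re-assessors.

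Three further points are fair. Both drivers of the calculation are assumed, and its upper end needs every participant affected; the 25-per-group column also needs no dropout. The double-blind description rests on participant blinding as well as evaluator blinding. Neutral IDs would not close every route: under section 6(d)(ii) participants record a training target in their log, and nothing says whether evaluators see it. None of these is a reason to keep the arm in the ID.

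**Conclusion.** The concern holds and should be fixed. Evaluator blinding is promised in three places, and the coding and access rules do not protect it. The documents do not show that any evaluator has been or will be unblinded.

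The textual gap is clear; its effect on the results is uncertain. With a quarter of participants affected, the false-positive rate stays near nominal, at most 6.3% (15 per group) or 7.2% (25 per group). It becomes material only if leakage is widespread. All these figures depend on the assumed coaching bias of 0.2 to 0.5 SD, and they concern inspiratory pressure and walk distance more than the other two primary outcomes.

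**What to change.** 1. In sections 6(e)(iv) and 10(a), replace the group-based code with an arm-neutral sequential ID, for example 001 to 050, assigned before allocation.
2. Keep the ID-to-arm list in its own password-protected file that only the investigator and the two weekly re-assessors can open.
3. In sections 6(e)(iv), 10(a) and 10(b), add: *Evaluators have no access to the allocation list or to any arm-labelled data until all final evaluations are complete.*

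Optionally, label the arms A and B in the analysis file. The statistical consultant could then fit the group-by-time model without the allocation list being shared.

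The cost is small: wording changes in three places, neutral IDs and one extra restricted file. No visits, measurements or participants are added, and sample size and significance level do not change.
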